2. STUDY DESIGN

Please refer to the study protocol for a full description of the trial design. This is a single-blind, pragmatic three-arm, parallel group, randomised trial. Participants will be recruited nationwide, using multi-media advertising with targeted promotion to reach Māori, Pacific and low socio-economic groups given their disproportionately higher smoking prevalence.

Potential participants interested in the trial will register on a trial website. Participants will be asked for on-line consent to complete an online screening questionnaire to determine their eligibility for the trial and verify their phone number. Eligible and interested participants will then provide online consent to enter the trial.

A copy of the consent form and participant information sheet will be automatically emailed by the online system to the participant for their records. Participants will also be asked to provide online consent to inform their general practitioner that they are participating in the trial. Via the online platform the baseline data will be collected, and then participants will immediately be randomised to either 12 weeks of: 1) cytisine plus nicotine e-cigarette, 2) cytisine; or 3) nicotine e-cigarette.

All 12-weeks of trial products will be couriered to participants immediately after randomisation. The courier company will notify the study centre immediately after the courier pack has been delivered, which will trigger the scheduling of the 'quit date' follow-up call and the start of the text-based behavioural support programme. Participants will be asked to begin their treatment the day after they receive their courier pack and to reduce their smoking *ad libitum* over the first four days of treatment so that they are not smoking at all by the fifth day ('quit date').

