2.3. Randomisation

All participants who fulfil eligibility criteria will be randomly allocated in a 3:3:2 ratio to one of the 3 treatment groups using block randomisation, and stratified by ethnicity (Māori, non-Māori). The randomisation sequence will be prepared by the study statistician and loaded into a secure database.

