2.4. Sample size

A sample size of 800 (N=300 in the cytosine group, N=300 in the cytosine plus nicotine e-cigarette group, and N=200 in the nicotine e-cigarette group) will provide 90% power at two-sided $p=0.05$ to detect an absolute difference of 13% in six-month smoking abstinence rates between the combination treatment group and the cytosine group, and 16% difference between the combination treatment group and the nicotine e-cigarette group (taking account of multiple testing).

The predicted difference is based on trial evidence for six month verified continuous abstinence quit rates of 9% for nicotine e-cigarettes, 12% for cytosine, and 25% for combination cessation treatment (averaged). The sample size accounts for a 28% loss-to-follow-up at six months.

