4.2. Secondary outcomes

The following secondary outcome measures will be collected over the phone on the quit date and at one, three, six and 12 months post-quit date:

- **Continuous abstinence** rates (using Russell standard) defined as self-report of smoking not more than five cigarettes in total from quit date (not collected at quit date)

Note if previous follow-up forms state they smoke more than 5 cigarettes since Quit date then subsequent follow-ups will be set to Not quit. Also, if a follow-up form is missing but the subsequent follow-up form(s) says they have smoked less than 5 cigarettes since Quit date (and no other previous follow-up forms have said they smoke more than 5 cigarettes since Quit date), then the missing follow-up form will have continuous abstinence set to 'Quit'.

- **Seven-day self-reported point prevalence abstinence** rates defined as no cigarettes, not even a single puff in the last seven days (not collected at quit date)
- **Change in average number of cigarettes smoked per day (CPD)** for participants still smoking
- **Proportion of participants who have significantly reduced smoking level** defined as reducing consumption by at least 25% (in terms of numbers of cigarettes per day)
- **Time to first lapse** (six and 12 months) defined as time to first cigarette smoked (even a single puff). From first follow-up form with question "Have you smoked any cigarettes at all in the last seven days, even a single puff?" equal to "Yes". Duration is calculated as the days since actual quit day to date of first lapse in the follow-up form.

Participants that withdraw will be censored on the last available visit, and participants that have not lapsed by the six (or 12) month follow-up will be censored on the six (or 12) months visit date. Note the first follow-up form with a lapse date will be taken since this will be more accurately remembered by participants than later visits.

- **Time to first relapse** defined as time to smoking more than five cigarettes a day for three or more days in a row. From first follow-up form with question “Have you smoked more than 5 cigarettes per day for 3 or more days in a row?” equal to “Yes”. Duration is calculated as the days since actual quit day to date of first relapse in the follow-up form

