7.5. Primary outcome analysis

The proportion of participants that have been biochemically verified as continuously abstinent at six months by group will be analysed using log-binomial regression, and the risk in each group, relative risks, absolute risk differences, and corresponding 95% confidence intervals will be calculated. All analyses for the

primary outcome will be ITT (unless otherwise stated) and include all randomised participants. Missing outcomes will be imputed using multiple imputation assuming the data is missing at random. Multiple imputed datasets will be created (n=50) and the imputation model will include baseline age, sex, and group, and the fully conditional specification logistic regression method will be used to impute the missing outcomes. The imputed datasets will be analysed using log-binomial regression and combined to output one inference. Adjusted analyses for potential covariates will be conducted if needed.

To check the robustness of the primary outcome the following sensitivity analyses will be conducted:

- self-reported continuous abstinence at 6 months (not biochemically verified)
- using the following varying cut-offs used for CO measurements: ≤ 3 ppm, ≤ 5 ppm, ≤ 8 ppm

The following sensitivity analyses will also be conducted for the primary outcome where groups will be compared using chi-squared tests:

- complete case analysis
- per protocol analyses where participants that have any major protocol violations will be excluded (see 6.2)
- assuming all missing outcomes are still smoking instead of using multiple imputation

Tests for heterogeneity will be used to examine if there is any difference in the groups on the unadjusted primary outcome for the following subgroups: baseline age (will be dichotomised based on the median), sex, ethnicity (Māori, non-Māori), education (< 12 years of attending school, 12 or more years of attending school), type of cigarettes smoked (RYO, factory made, both), AUDIT-C (low, high), cannabis use, motivation to quit, level of cigarette dependence (using HSI), and level of behavioural support received (will be categorised based on the data). Subgroup analyses will also be conducted by batch number of product received (Batch 1: early 2022, Batch 2: early 2023) to assess if there were any differences by batch.

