7.6. Secondary outcomes analysis

Descriptive summary statistics for each follow-up visit and group will be presented for all secondary outcomes. For all secondary outcomes (unless otherwise stated) participants with missing outcome data will be excluded from the analyses.

Incidence rates, risk difference, relative risks and 95% confidence intervals will be calculated for self-reported continuous abstinence (not biochemically verified), seven-day point prevalence abstinence and reduced CPD consumption by at least 50% outcomes at each follow-up visit. Both complete case analysis and ITT analysis (where missing outcomes will be imputed using the same multiple imputation method described above for the primary outcome) will be conducted.

MPSS at 3 months (for 6-month continuous abstainers only) will be analysed using linear regression and include baseline MPSS in the model. The change from baseline in each of the repeated continuous outcomes (average number of cigarettes smoked each day for smokers, weight and BMI) will be analysed using mixed models. Each model will include group and the baseline measure. The appropriate covariance structure to be used will be assessed by the likelihood ratio test. The method of maximum likelihood will be employed to ensure patients with missing data are included in the model assuming the data is missing at random. However, if all follow-up data is missing then the participant will be excluded from the analyses. Intervention by visit interaction effects will be tested. Note the

distribution of these continuous outcomes will be first assessed for normality and skewed data will be subjected to an appropriate transformation before analysis. Non-parametric analysis (Mann-Whitney tests) will be used for the continuous outcomes if data is skewed and cannot be transformed to be normally distributed.

The time to first lapse and relapse outcomes will be analysed using Kaplan-Meier curves, the log rank test, and Cox proportional hazards regression analysis.

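### By default the subgroup heterogeneity tests in SAP 7.5 use outcomes imputed from age, sex and group only, which makes them conservative for the seven baseline factors outside that model

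*SAP*

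**What the plan says.** SAP 7.5 sets a general rule: analyses for the "primary outcome will be ITT (unless otherwise stated) and include all randomised participants". Missing outcomes are filled in by 50 imputations under a missing-at-random assumption, and "the imputation model will include baseline age, sex, and group". No other covariate and no interaction is listed.

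The same section then plans tests of heterogeneity "on the unadjusted primary outcome for the following subgroups". Nine of these are baseline factors: age, sex, ethnicity, education, cigarette type, AUDIT-C, cannabis use, motivation and HSI. Level of behavioural support received and product batch are also listed, but this point does not cover them. The sentence does not say whether the tests use imputed or observed outcomes.

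Two places bear on the default. In 7.5, complete case appears only among the chi-squared sensitivity analyses of the group comparison. In 7.6, complete case is set against "ITT analysis (where missing outcomes will be imputed using the same multiple imputation method described above for the primary outcome", so ITT and imputation go together.

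Allocation is "stratified by ethnicity (Māori, non-Māori" (SAP 2.3), and recruitment uses "targeted promotion to reach Māori, Pacific and low socio-economic groups" (SAP 2). On missing data, SAP 2.4 states: "The sample size accounts for a 28% loss-to-follow-up at six months".

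**The concern.** A heterogeneity test asks whether the treatment effect differs between subgroups. If the imputation model lacks the subgroup factor and its interaction with group, every imputed outcome is drawn as if the effect did not differ. Missing at random does not cure this, because the test contains a term that the imputation model sets to zero. Two things follow. The estimated contrast is pulled toward zero. Rubin's variance is also larger than the true sampling variance, so the test rejects too rarely even when there is no heterogeneity.

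What is at stake is how the subgroup results can be read. Ethnicity is the only stratification factor and Māori are a named recruitment target, so readers will look at that test first. A finding of no heterogeneity would be partly produced by the imputation.

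**Working it through.** **The plan's own figure.** The SAP gives no power for the subgroup tests. Its main figure (SAP 2.4) is 90% power for 25% v 12% with 300 per arm and 28% loss. With 300 × 0.72 = 216 evaluable per arm, two-sided 0.025 (0.05 split over two comparisons) gives 89.5% and a requirement of 306 per arm, so the figure is reproduced. Unsplit 0.05 gives 93.8%.

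**Inputs.** From the SAP: 300/300, 25% v 12%, 50 imputations, 28% planned loss. Assumed: the imputed share f (28% is a planning allowance, so a range is shown); 40% Māori, hence 180 and 120 per arm; equal loss in both ethnic groups. The null has the same rates in both ethnic groups. The alternative has combination 30% in non-Māori and 17.5% in Māori (0.6 × 30 + 0.4 × 17.5 = 25%) and cytisine 12% in both. The true contrast is 12.5 points.

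**Shrinkage for a factor outside the model.** Imputed outcomes carry the arm-average rate in both subgroups, so each subgroup rate becomes (1−f) × true rate + f × arm average. At f = 0.28:
- non-Māori: 0.72 × 0.30 + 0.28 × 0.25 = 0.286
- Māori: 0.72 × 0.175 + 0.28 × 0.25 = 0.196
- contrast: 0.286 − 0.196 = 0.090 instead of 0.125, that is 0.72 of its true value.

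In general the risk-difference contrast keeps 1−f. On the log relative-risk scale, ln(0.286/0.196) / ln(0.30/0.175) = 0.70.

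**Type I error.** Let V be the variance of the contrast with complete data. The observed part contributes (1−f)² × V/(1−f), so the true sampling variance is about (1−f)V. Rubin's variance is about V + fV = (1+f)V. The ratio of true to reported SE is √((1−f)/(1+f)). At f = 0.28 this is √(0.72/1.28) = 0.75, so the effective critical value is 1.96/0.75 = 2.61 and the true size is 0.009.

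**Power.** V = 0.30×0.70/180 + 0.175×0.825/120 + 0.12×0.88/180 + 0.12×0.88/120 = 0.003836, so √V = 0.0619. At f = 0.28:
- Complete case: SE = 0.0619/√0.72 = 0.0730. Then 0.125/0.0730 = 1.71, and power = P(Z > 1.96 − 1.71) = 0.40.
- Imputed: the rejection limit is 1.96 × 0.0619 × √1.28 = 0.137, the mean is 0.090 and the true SE is 0.0619 × √0.72 = 0.0526. Power = P(Z > (0.137 − 0.090)/0.0526) = 0.18.

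**Simulation** (risk difference, group-only imputation, 50 imputations, Rubin's rules, 4000 null and 3000 alternative trials per point) agrees:

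| Imputed share | Contrast kept | Type I, imputed | Type I, complete case | Power, imputed | Power, complete case |
|---|---|---|---|---|---|
| 10% | 0.90 | 0.029 | 0.051 | 0.39 | 0.47 |
| 20% | 0.80 | 0.018 | 0.052 | 0.28 | 0.44 |
| 28% | 0.72 | 0.011 | 0.056 | 0.19 | 0.42 |
| 35% | 0.65 | 0.004 | 0.053 | 0.11 | 0.38 |

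Repeat runs at 28% gave type I error 0.008 and power 0.17 v 0.40. A separate simulation of 1500 runs, with age and sex also in the imputation model, gave type I error 0.005 at 28%. Adding the group-by-ethnicity term restores type I error to 0.054 and power to 0.41 at 28%.

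**Age and sex.** These have a main effect in the imputation model but no interaction. At 28% the risk-difference contrast keeps 0.80 in the base scenario and 0.91 when cytisine abstinence is 14% v 9%. It keeps 1.00 when the odds ratio is common to both subgroups. On the log relative-risk scale the range is 0.50 to 1.00. The 0.50 is unstable, because the true ratio of relative risks in that scenario is only 1.10. In the base scenario the test is still conservative (type I error 0.031 at 10% and 0.014 at 28%).

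**The case against.** **The data set is an inference.** The heterogeneity sentence follows the chi-squared sensitivity list, mentions no pooling over imputations, and may be settled by the separate file of table shells (SAP 7, Appendix I), which is not at hand. If observed outcomes were meant, the problem does not arise. This stands as a condition. But 7.5 states a default and no exception, and "unadjusted" concerns covariates rather than missing data, so the plan as written leads to imputed data.

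**The size is uncertain.** SAP 4.2 says that after an earlier report of more than five cigarettes "subsequent follow-ups will be set to Not quit". That rule is written for self-reported continuous abstinence. Applied to the primary outcome, it would leave fewer outcomes to impute, while missing CO readings would leave more. This stands: the imputed share is unknown, and at 10% the effect is mild.

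**The consequence is small.** No stated decision rests on these tests, and power is only about 0.4 at 28% loss even when they are done well. A non-significant result would be weak evidence of a uniform effect in any case. This stands and limits the priority.

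**Stronger readings.** A reader might infer that all nine baseline contrasts shrink by the imputed share. They do not, because age and sex are in the imputation model. A reader might also infer that the main treatment comparison is biased. It is not materially affected, since group is in the imputation model.

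**Conclusion.** The point holds for seven baseline factors: ethnicity, education, cigarette type, AUDIT-C, cannabis use, motivation and HSI. Under the ITT default in 7.5, their risk-difference contrasts shrink by about the imputed share. Type I error falls to about 0.03 at 10% imputed and about 0.01 at 28%, and power at 28% is less than half that of complete cases. For age and sex the shrinkage depends on scale and scenario and can be nil.

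The direction follows from the imputation model. The size rests on the assumed imputed share, and the power figures also on the assumed 40% Māori share and 12.5-point alternative. Minor priority: it limits what the subgroup results can show, not the trial's main conclusion.

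**What to change.** In 7.5, name the data used for the heterogeneity tests.

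- **Simplest:** state that they use participants with an observed primary outcome. This costs one sentence, and its power matches corrected imputation (0.42 v 0.41 at 28%, with loss unrelated to outcome). The price is a departure from all-randomised ITT for these tests, and reliance on missingness at random given arm and subgroup.
- **Alternative, if imputed data are wanted:** impute within each arm with the subgroup factor included, or add the factor and its group-by-factor terms to the imputation model for that test. This means one imputation model per factor. With three arms, a two-level factor needs 2 group-by-factor terms and a three-level factor 4. Motivation, recorded on five levels (SAP 3), needs 2 × 4 = 8 unless grouped. Cells will be sparse: at an assumed 40% Māori, the e-cigarette arm has 200 × 0.40 × 0.72 = about 58 observed Māori participants and, at 9%, about 5 quitters. Penalised logistic imputation may be needed.

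Adding only the factor's main effect is not enough. In the base scenario at 28% imputed, the contrast kept rises only from 0.72 to 0.80 on the risk-difference scale and stays at 0.70 on the log relative-risk scale.

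### The complete-case, per protocol and missing-equals-smoking checks are specified as chi-squared tests, with no relative risk, risk difference or interval prespecified to set beside the primary estimate

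*SAP*

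**What the plan says.** SAP section 7.5 states that the primary outcome "will be analysed using log-binomial regression", and lists what comes out of it: "the risk in each group, relative risks, absolute risk differences, and corresponding 95% confidence intervals will be calculated".

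Two lists of sensitivity analyses follow. The first (self-reported abstinence and the alternative CO cut-offs) changes the outcome definition and says nothing about a new method. The second is introduced differently, as analyses "where groups will be compared using chi-squared tests". It has three items: a "complete case analysis", a per protocol analysis, and an analysis "assuming all missing outcomes are still smoking instead of using multiple imputation". No relative risk, risk difference or interval is named for these three.

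Three other places bear on this:

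- Section 6.2 gives checking robustness as the purpose of the per protocol analysis.
- Section 7 says that categorical variables are shown as frequencies and percentages. It fixes two comparisons (combination vs cytisine, combination vs e-cigarette), but states them for regression analyses.
- Section 7.6 specifies risk difference, relative risk and 95% intervals for the binary secondary outcomes, under both complete-case analysis and multiple imputation.

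**The concern.** A sensitivity analysis asks how far the estimate, and the uncertainty around it, moves when an assumption changes. That calls for the same effect measure with an interval in each analysis. A chi-squared test answers a different question: whether the data are compatible with no difference. Its p-value depends on the size of the set as well as on the effect.

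This matters most for missing data. The primary analysis imputes missing outcomes under a missing-at-random assumption, and section 2.4 expects 28% loss. The complete-case and missing-equals-smoking analyses are the checks in section 7.5 that handle those missing outcomes differently, and they are the ones left without a prespecified estimate. The primary outcome's own complete-case check is therefore less fully specified than the complete-case analyses of the secondary outcomes.

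There is also a gap in the contrasts. A chi-squared test is not a regression, so the rule in section 7 that fixes the two pairwise comparisons does not plainly cover it. With three arms, the text can be read as pairwise tests or as one three-group test. A three-group result could not be set beside either primary contrast.

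**Working it through.** **Inputs from the SAP.** Arms of 300 (combination), 300 (cytisine) and 200 (e-cigarette); abstinence 25%, 12% and 9%; 28% loss; 90% power (section 2.4).

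**Assumptions.** Two-sided alpha of 0.025 for the SAP's allowance for multiple testing; whole-number counts; Pearson chi-squared without continuity correction; Wald intervals.

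**1. The plan's own figure.** Evaluable per arm: 300 × 0.72 = 216. With pooled variance under the null, z = [0.13 × √216 − 2.241 × √(2 × 0.185 × 0.815)] / √(0.25 × 0.75 + 0.12 × 0.88) = (1.911 − 1.231) / 0.541 = 1.26. Power is 89.5%, against 90% stated. Combination vs e-cigarette (216 vs 144 evaluable) gives 96.0%. The design figures are reproduced, and nothing in this point alters them.

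**2. Equal 28% loss.** The numbers of abstainers are 0.25 × 216 = 54, 0.12 × 216 ≈ 26 and 0.09 × 144 ≈ 13. Counting missing as smoking leaves these unchanged and restores the randomised denominators.

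Formulas: RR = p1/p2, with SE(log RR) = √(1/x1 − 1/n1 + 1/x2 − 1/n2). RD = p1 − p2, with SE = √(p1q1/n1 + p2q2/n2). Intervals are ±1.96 SE.

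| Contrast and set | Counts | chi² | p | RR (95% CI) | RD, points (95% CI) |
|---|---|---|---|---|---|
| vs cytisine, complete case | 54/216 vs 26/216 | 12.03 | 0.0005 | 2.08 (1.35 to 3.19) | 13.0 (5.7 to 20.2) |
| vs cytisine, missing = smoking | 54/300 vs 26/300 | 11.31 | 0.0008 | 2.08 (1.34 to 3.22) | 9.3 (3.9 to 14.7) |
| vs e-cigarette, complete case | 54/216 vs 13/144 | 14.55 | 0.0001 | 2.77 (1.57 to 4.89) | 16.0 (8.5 to 23.4) |
| vs e-cigarette, missing = smoking | 54/300 vs 13/200 | 13.68 | 0.0002 | 2.77 (1.55 to 4.94) | 11.5 (6.0 to 17.0) |

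With equal loss the RD shrinks by the factor 216/300 = 0.72 and the RR does not move. The p-value hardly changes.

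**3. Unequal loss (assumed 20% in combination, 36% in cytisine; average 28%).** Denominators are 240 and 192.

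- Complete case: 60/240 vs 23/192, p = 0.0006, RR 2.09, RD 13.0.
- Missing = smoking: 60/300 vs 23/300, p = 0.00001, RR 2.61, RD 12.3.

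Here the RR rises and the RD falls slightly, while p drops sharply. In neither scenario does the p-value tell the reader which measure moved, or by how much.

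**4. Per protocol.** The SAP gives no expected size for this set, so no figure is offered.

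**The case against.** A reader might infer that these three analyses will yield nothing but a p-value, that they cannot show whether the answer moved, and that the SAP will judge robustness by whether p stays below 0.05. The document does not support any of these:

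- Section 7.5 says how groups are compared; it does not rule out other output. Under section 7, abstinence percentages per arm should be shown. In a model with group as the only term, the RR is their ratio and the RD their difference, so a crude estimate can be read off.
- No rule in the SAP declares robustness by a p-value threshold.
- The table shells are in a separate file (Appendix I) that is not shown. They may contain columns for estimates.

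Nor is frequent loss of significance a strong argument for the two missing-data checks. At the planned rates and two-sided 0.05, power is 93.8% for complete case (216 per arm). For missing = smoking (300 per arm, 18% vs 0.72 × 12% = 8.64%) it is about 92%: z = (0.0936 × √300 − 1.96 × 0.4805) / 0.4760 = 1.43.

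It is also true that, for an unadjusted two-arm comparison, chi-squared and log-binomial regression address the same null hypothesis. The test is valid.

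What remains is narrower. The text prespecifies no effect measure and no interval for these checks, it does so for less important outcomes, and it does not say which groups each test compares.

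**Conclusion.** The point holds as one of specification and reporting. Three robustness checks on the primary outcome are set up as tests, without the relative risk, risk difference and interval that the primary analysis and the binary secondary outcomes receive, and with the contrasts left open.

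Its size is shown by the combination vs cytisine illustration: p goes from 0.0005 to 0.0008 while the RD falls by 3.6 points, from 13.0 to 9.3. That rests on the SAP's planning rates, equal 28% loss and rounded counts; the unequal-loss version rests on an assumed split.

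The severity is low. Nothing here is an error in the primary analysis, and its estimate, the alpha level and the sample size are untouched.

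**What to change.** In SAP section 7.5, replace the chi-squared wording for the second list. State that the complete-case, per protocol and missing-equals-smoking sets will be analysed with the same log-binomial model as the primary analysis (unadjusted, unless the primary is adjusted), for the same two pairwise contrasts as in section 7. Report the risk in each group, relative risk, risk difference and 95% CI for each. The chi-squared p-value can be dropped or kept beside them. Check that the Appendix I tables have matching columns.

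The cost is a sentence or two of SAP text and a rerun of the existing program on three data sets. No new data are needed.

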2.1. Eligibility criteria

Participants will be eligible for inclusion if they:

- Are daily smokers who live in New Zealand
- Are at least 18 years of age
- Want to quit smoking in the next 2 weeks
- Are able to provide online consent
- Have access to a mobile telephone that can text and have access to the internet via a computer or smart phone
- Are willing to use cytisine or an e-cigarette or both products to help quit smoking

Exclusion criteria:

- Are pregnant or breastfeeding or if they are women trying to become pregnant in the next three months
- Currently using smoking cessation medication (including daily use of an e-cigarette for the last month)
- Are enrolled in another smoking cessation program or trial
- Have known hypersensitivity to cytisine, or nicotine e-cigarettes
- Have a strong preference to use or not to use cytisine and/or e-cigarettes in their quit attempt
- Self-report that they have moderate or severe renal impairment, are undergoing treatment for active or latent tuberculosis, have experienced a myocardial infarction, stroke, or severe angina within the previous two weeks, have uncontrolled high blood pressure (>150 mmHg systolic, >100 mmHg diastolic) or have a history of seizures
- Have another person in their household involved in the trial

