3. BASELINE DATA

The following baseline data will be collected online via the trial website:

- **Demographic information:** Date of birth, gender, ethnicity, and level of education. Also self-reported height and weight, and body mass index (BMI) will be calculated.
- **Smoking history:** Age when started, number of cigarettes smoked per day, number of years as regular smoker, number of previous attempts to give up in past 12 months (and the longest time they stayed quit and the method used), type of cigarettes smoked per day (e.g. roll-your-own or factory-made) and pack size and how long pack lasts (for roll-your-own users), and whether they had cut down the number of cigarettes they smoked in the past 12 months.

- **Motivation to quit** in the next two weeks, measured using a five-point Likert Scale, where 1=very low motivation and 5=very high.
- **Level of cigarette dependence:** will be determined using the Heaviness of Smoking Index (HSI), which is a two-item measure based on the number of cigarettes smoked per day (categorised as: 0=10 or fewer, 1=11-20, 2=21-30, 3=31 or more) and the time to first cigarette of the day. The HSI total score is calculated by summing these two items and has range 0 to 6 where higher scores indicate greater dependence severity. The HSI total score will be categorised as low addiction (0-2), moderate addiction (3-4) and high addiction (5-6).
- **Other smoking related information:** household smoking, self-rated chances of quitting (measured using a five-point Likert Scale, where 1=extremely low and 5=extremely high), and whether they are around others that use e-cigarettes.
- **General Health:** Self-reported shortness of breath, cough, asthma, chronic pain, and Chronic Obstructive Pulmonary Disease (COPD), and current or history of mental health (including depression, schizophrenia, and anxiety).

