- **Alcohol use:** Measured using the Alcohol Use Disorders Identification Test (AUDIT-C). The AUDIT-C score is calculated by summing all three items and has range 0 to 12 where higher scores indicate greater risk of alcohol dependence. Note participants that tick 'Never' for the first AUDIT-C item (How often do you drink alcohol in the past year) then skip the next two AUDIT-C items, so for these AUDIT-C score to be set to value 0. For men, an AUDIT-C score ≥ 4 indicates an increased risk of hazardous drinking or alcohol dependence, while in women it is a score of ≥ 3 . And an AUDIT-C score ≥ 8 indicates a very high risk for both men and women.
- **Health related quality of life:** measured using the NZ EQ-5D
- **Signs and symptoms of nicotine withdrawal and urge to smoke:** measured using the Mood and Physical Symptoms Scale (MPSS) which consists of the following:
 - 5-point ratings of depressed mood, irritability, restlessness, hunger and difficulty concentrating. MPSS score is calculated by summing all 5 items and has a range of 5 to 25 where higher scores indicate greater nicotine withdrawal.
 - 6-point ratings of time spent with urges to smoke and strength of urges to smoke. Note the strength of urges question has values 1 to 5. Participants who tick 'Not at all' for time spent with urges to smoke have to then skip to the next section of questions and don't answer the question on strength of urges. So for these participants need to set strength of urges to equal value 0. [Therefore, this question will then have values 0 to 5]. The urge score is calculated by summing the two urges questions and has a range 0 to 10 where higher scores indicate greater urge to smoke.
- **Cannabis use:** Participants will be asked if they have used cannabis for recreational or non-medical purposes in the last 12 months.

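### The SAP tests heterogeneity on split or banded versions of age, AUDIT-C and HSI, which discards recorded information; for age the loss is about 25% to 45% if modification is linear

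*SAP*

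**What the plan says.** SAP section 7.5 plans heterogeneity tests on the unadjusted primary outcome for a list of subgroups. The entries that concern us are:

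- **Age:** "baseline age (will be dichotomised based on the median".
- **Scores:** "AUDIT-C (low, high), cannabis use, motivation to quit, level of cigarette dependence (using HSI".

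Section 3 says how the scores are recorded and, for one of them, grouped:

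- **HSI** runs from 0 to 6. "The HSI total score will be categorised as low addiction (0-2), moderate addiction (3-4) and high addiction (5-6". Section 7.5 refers to a level of dependence, so I read these three bands as the subgroups.
- **AUDIT-C** runs from 0 to 12. Section 3 gives a sex-specific threshold (4 or more for men, 3 or more for women) and a higher one: "And an AUDIT-C score ≥ 8 indicates a very high risk for both men and women". Section 7.5 does not say which of these separates low from high.
- **Motivation** is "measured using a five-point Likert Scale, where 1=very low motivation and 5=very high". Neither section gives a grouping.

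Age is limited only by "Are at least 18 years of age" in section 2.1. The SAP gives no expected distribution for age or for any of these scores, and it plans no interaction with a value as recorded.

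**The concern.** Age is continuous, and AUDIT-C and HSI are ordered scores. Splitting or banding them before testing treats everyone within a group as identical, so the gradient within each group contributes nothing to the test. For age, the boundary is also unknown until recruitment ends and has no meaning outside this sample, which makes the result hard to compare with another trial.

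These tests have little power to spare. Section 2.4 sizes the trial for main effects, at expected abstinence of 25%, 12% and 9%. Among those randomised, before any loss, that is 300 × 0.25 = 75, 300 × 0.12 = 36 and 200 × 0.09 = 18 abstainers. An interaction test on so few events is weak already, and a further avoidable loss makes a null result less informative. What is at stake is the reading of the subgroup results only.

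**Working it through.** **The plan's own figure.** The SAP states no power for the heterogeneity tests. The nearest figure is the 90% power in section 2.4 for the main comparisons. With 28% loss, 300 becomes 216 and 200 becomes 144. Taking the allowance for multiple testing as a two-sided 0.025:

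- 25% v 12%, 216 per arm: 89.5% power, in agreement with the stated 90%.
- 25% v 9%, 216 and 144: 96.0%, so the stated 90% is conservative.

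This confirms that the trial was sized for main effects; it says nothing about interactions.

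**Information kept by a median split of age.** For a linear modifier, the share kept is the squared correlation between recorded age and the above-median indicator. The age shapes are assumptions.

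| Assumed age distribution | Kept | Lost |
|---|---|---|
| Uniform | 0.750 | 25% |
| Normal, cut off at 18 and 80 (mean 42, SD 13) | 0.661 | 34% |
| Normal | 2/π = 0.637 | 36% |
| Right-skewed (18 + gamma, shape 4) | 0.594 | 41% |
| More right-skewed (18 + gamma, shape 2) | 0.554 | 45% |

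**Effect on power.** If the test on recorded age has power Φ(z), the test after the split has power Φ(√kept × (1.96 + z) − 1.96).

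- From 80% (z = 0.842, sum 2.802): normal, 0.798 × 2.802 − 1.96 = 0.275, giving 61%; uniform, 0.866 × 2.802 − 1.96 = 0.466, giving 68%.
- From 50% (z = 0, sum 1.96): normal, 0.798 × 1.96 − 1.96 = −0.396, giving 35%; uniform, 0.866 × 1.96 − 1.96 = −0.263, giving 40%.

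**Check by simulation.** 300 v 300, baseline 12% and 25%, logistic model, 600 replicates (Monte Carlo error about 2 points), interaction sizes assumed.

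| Log-odds interaction per SD | Age shape | Recorded age | Median split |
|---|---|---|---|
| 0.5 | Normal | 53% | 39% |
| 0.5 | Uniform | 59% | 48% |
| 0.7 | Normal | 83% | 62% |
| 0.7 | Uniform | 86% | 75% |

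The drops agree with the formula.

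**AUDIT-C and HSI.** Both groupings also discard recorded order and distance, but the age figures do not carry over: neither is cut at its median, and the SAP gives no distribution for either. I put no figure on their loss. Low/high AUDIT-C uses one degree of freedom per treatment comparison, as median-split age does. HSI in three bands uses two, against one for the score.

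**Motivation.** The coding is open. If it entered as five categories, the number of abstainers at low levels would depend on an unknown distribution. In the e-cigarette arm (200 randomised, 9% abstinent):

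- Assumed shares of 1% at level 1 and 4% at level 2 put 2 and 8 participants there; the chance of no abstainer is 0.91² = 83% and 0.91⁸ = 47%.
- An even 20% at each level puts 40 participants there; the chance is 0.91⁴⁰ = 2%.

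**The case against.** The case for leaving the text alone is reasonable. The median is computed from baseline data without sight of outcomes, and the rule is stated in advance. The HSI bands are fixed, and section 3 supplies interpretable AUDIT-C thresholds. The loss for age depends on linearity: if the effect really stepped at the median, the split would be the better test, by the same factor. A test that starts with little power also loses little in absolute terms; by the formula above, 20% falls to about 14% for normal ages. Finally, log-binomial models can fail to converge with continuous covariates, because fitted risks must stay below 1.

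Most of this stands as a limit on importance. It does not rescue the choice. A step exactly at this sample's median is a less plausible default than a gradual change, and the categories remain available as a check.

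A reader might go further and infer that motivation will be too sparse to estimate, since entry requires that participants "Want to quit smoking in the next 2 weeks". The SAP does not support that. It does not say that motivation enters as five categories, it gives no distribution, and wanting to quit makes low scores plausibly rare without showing that they are. Empty cells are a possibility under one coding, no more. A reader might also infer that all these groupings spend extra degrees of freedom; for age and AUDIT-C they do not.

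**Conclusion.** The point holds as a modest improvement to the subgroup tests. Section 7.5 fixes a less efficient test than the recorded data allow. For age, the loss is about 25% (uniform) to 36% (normal), and up to about 45% for skewed ages, which would take an 80% test to about 61-68% in the uniform and normal cases. These figures assume approximately linear modification and an age distribution that the SAP does not give, and they apply to age alone. For AUDIT-C and HSI the direction is the same but the size is not established. For motivation the only fault in the text is that the coding is unstated. The primary estimate and its confidence interval are unaffected, so this is desirable rather than necessary.

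**What to change.** Amend section 7.5 so that, for each treatment comparison:

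1. The heterogeneity test for age, AUDIT-C and HSI is a one-degree-of-freedom interaction between group and the value as recorded.
2. Motivation enters in the same way, as its 1-5 score.
3. The median split of age, the AUDIT-C low/high groups and the HSI bands are kept for the forest plot and as a check on linearity. The text should say which section 3 threshold defines low and high AUDIT-C.
4. A fallback, such as modified Poisson regression, is named in case the log-binomial model does not converge.

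The cost is wording; all the data are already collected at baseline. The price in method is the assumption of an approximately linear interaction. A strongly non-linear pattern could be missed by the single term, which is why the categorical display should stay. If AUDIT-C is read on its sex-specific threshold, the raw score is also not quite the same quantity as the low/high grouping, and the report should say so.
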